#### 4.1.2 Secondary Efficacy Endpoint

Secondary efficacy endpoints are the following:

- **Time to last unformed stool (TLUS)**

TLUS is defined as the interval beginning with the first dose of study drug and ending with the last unformed stool passed within a period of 120 hr. (last dose which is 72hrs, plus 48hrs).

Mathematically, TLUS will be calculated as follows:

TLUS (hours) = date/time of last unformed stool within 48hrs from the time of last dose – date/time of first dose

- **Microbiological cure rate**

Subjects are considered to have achieved microbiological cure if the pathogen identified at Visit 1 is no longer found in the stool at the TOC visit. Microbiological cure rate will be a supportive evidence of similarity between the test product and the reference product treatment arms and not considered as evidence of clinical bioequivalence.

#### 4.2 Safety Endpoints

The safety endpoints are:

1. Number and proportion of subjects reporting adverse events
2. Changes in clinical laboratory tests, vital signs, and physical examinations from baseline
3. Prior or Concomitant Medication
4. Medical History
5. Enteric symptoms

## 5. ANALYSIS POPULATION

### 4.3 Randomized population

Randomized population includes all the subjects who satisfies the inclusion and exclusion criteria and randomized into the study. This population may contain subjects who were randomized and have not consumed any drug. The assigned treatment group is used for the analysis.

[figure not shown]

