### 4.4 Safety Population

All randomized subjects who receive at least one dose of study drug will form the Safety Analysis Set. The Safety Analysis Set will be used for all analyses of safety, tolerability, and background characteristics.

[figure not shown]

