### **8.1 Subject Accountability and Disposition**

The subject accountability and disposition information will be summarized for each treatment group. The subject accountability may include and not limited to number of subjects screened, enrolled, randomized, treated, discontinued before study completion and study completed. The subject disposition may include number of subjects in each population, study completion status and primary reason for discontinuation from the study. These summary reports will be generated using all randomized population and grouped by randomized treatment with total as a separate column.

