#### **8.6 Protocol deviations**

The following describes the protocol deviations that relate to statistical analyses or Per-protocol population.

All deviations related to study inclusion and exclusion criteria and significant deviations to subject management and protocol procedures must be documented on the appropriate eCRF. Major protocol deviations/violations will include, but are not limited to, the following:

- Did not meet any critical inclusion/exclusion criteria which may impact the assessment of treatment efficacy.
- Did not receive randomized treatment (i.e., the actual treatment is not randomized treatment).
- Use of prohibited concomitant medications (e.g., prescription or OTC anti-diarrheal drug product, NSAIDs [with the exception of acetaminophen and paracetamol] or opioid analgesics).
- Did not meet the drug compliance of taking  $\geq 7$  to  $\leq 11$  doses.
- Did not come for Visit 3 or did not provide efficacy data for 24 hour to 48 hour period after the last dose.

A list of protocol deviations will be compiled prior to database closure for the primary analysis

and be updated prior to the analysis. The deviations will be listed on randomized population and also will be summarized on randomized population by treatment group.

[figure not shown]
Further, all the protocol deviations will be manually reviewed by the medical monitor of the study to determine whether any deviation is significant with respect to per-protocol population. Such deviations which may affect the treatment evaluation would be declared as “significant” protocol deviation by the medical monitor, and consequently these subjects will also be excluded from the per-protocol population for the primary efficacy analysis, in addition to above mentioned protocol deviations.

The medical monitor will send the significant protocol deviations to Biostatistics team in an excel sheet through email before DB lock. All these significant protocol deviations will also be submitted to regulatory in the form of XPT file along with the protocol deviations captured in the eCRF. The additional list of these protocol deviations will be prepared with respect to per-protocol population criteria and will be listed on randomized population by treatment group.

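### The SAP limits the randomized population to eligible subjects, yet reports protocol deviations, including eligibility failures, on that same population

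*SAP*

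**What the plan says.** The definition is in the SAP's Analysis Population section, under Randomized population (numbered 4.3 in the body, 5.1 in the table of contents): "Randomized population includes all the subjects who satisfies the inclusion and exclusion criteria and randomized into the study". It continues: "This population may contain subjects who were randomized and have not consumed any drug". The group is analysed by assigned treatment.

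SAP 8.6 (Protocol deviations) puts this first among the major deviations: "Did not meet any critical inclusion/exclusion criteria which may impact the assessment of treatment efficacy". On reporting it states: "The deviations will be listed on randomized population and also will be summarized on randomized population by treatment group". The medical monitor's further list of significant deviations uses the same set: "The additional list of these protocol deviations will be prepared with respect to per-protocol population criteria and will be listed on randomized population by treatment".

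SAP 8.1 (Subject Accountability and Disposition) says: "These summary reports will be generated using all randomized population and grouped by randomized treatment with total as a separate column".

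The safety set has no eligibility condition: "All randomized subjects who receive at least one dose of study drug will form the Safety Analysis Set". The mITT set takes all randomized subjects and then requires that they meet every inclusion criterion and no exclusion criterion.

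Protocol section 9.2 defines three analysis sets, none of them a randomized set. Protocol 9.3 uses a randomized population for screening and baseline summaries without attaching an eligibility condition to it.

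**The concern.** A deviation table is where a reader looks to see how many subjects were randomized in error, and whether the arms differ in this. If the set behind the table already requires eligibility, the table will show no eligibility failures whatever happened at the sites. Any other deviations in those subjects drop out with them.

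The definition also breaks the usual order of the sets, in which everyone dosed is a subset of everyone randomized. At stake are the accuracy of the deviation outputs and the reconciliation of set sizes in the study report, not the efficacy conclusions.

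**Working it through.** The plan states no figure to reproduce here. The check is on the sets that the text defines.

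**Step 1. Split all randomized subjects into four groups.**
- *a*: eligible, dosed
- *b*: eligible, not dosed
- *c*: ineligible, dosed
- *d*: ineligible, not dosed

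**Step 2. Apply the SAP definitions as written.**

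| Set | Condition in the SAP | Content |
|---|---|---|
| Everyone randomized | none | a + b + c + d |
| Randomized population | randomized and eligible | a + b |
| Safety population | randomized and dosed | a + c |
| mITT | eligible, dosed, with post-dose data | part of a |

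The definition explicitly admits *b*, the undosed. It has no matching allowance for *c* or *d*.

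**Step 3. Deviation tables (SAP 8.6).** Subjects who failed a criterion are *c* + *d*. None of them is in *a* + *b*, so the count in the eligibility row is 0 by construction. The 8.6 item covers only critical criteria, while the population condition covers all of them. A subject who failed a lesser criterion is therefore also outside the set. The medical monitor's additional list has the same gap.

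**Step 4. Nesting.** Group *c* is in the safety set but not in the randomized set. The difference in size is (a + c) − (a + b) = c − b. If more ineligible subjects are dosed than eligible subjects are left undosed, the safety N exceeds the randomized N.

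**Step 5. Consistency with the mITT definition.** The mITT rule applies eligibility to all randomized subjects. That step would be redundant if being randomized, in the SAP's sense, already meant being eligible. The mITT wording therefore presupposes a randomized group that includes *c* and *d*.

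**Step 6. Possible size.** The documents give no ineligibility rate, so the rates below are assumptions applied to the planned 618:
- 1%: 618 × 0.01 = 6.2, about 6 subjects
- 2%: 618 × 0.02 = 12.4, about 12 subjects
- 5%: 618 × 0.05 = 30.9, about 31 subjects

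These are counts missing from the deviation outputs. They are not changes to any test or estimate.

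**The case against.** The best defence is that the sentence describes the route into the study, not a filter. It says the population includes eligible randomized subjects, not that it is confined to them, and Protocol 6.2 likewise says that eligible subjects are randomized. Sections 8.6 and the mITT definition both make sense only if ineligible subjects can be in the randomized group, so the authors probably expected them there. SAP 8.7 also promises a separate document, due before database lock or unblinding, on how the populations are derived. It is not available here and may settle the matter.

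This makes the intention plausible but does not remove the conflict. The sentence is the only definition the SAP gives, it states eligibility as an attribute of members, and it provides for one exception (no drug taken) but not the other. A programmer setting population flags from it would be entitled to exclude ineligible subjects.

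Other parts of the defence stand and limit the point. A reader might infer the following, and the documents do not support it:
- **That disposition tables will not add up to the number randomized.** SAP 8.1 speaks of the whole randomized population and also counts screened subjects, who cannot be in the defined set. It may well mean everyone randomized.
- **That the loss from randomized to mITT will be understated against the 15% in the plan.** The 15% is a sample-size assumption. The visible text plans no reported loss statistic on the defined set and ties no decision to one.
- **That the subjects disappear from the record.** SAP 8.6 requires eligibility deviations in the eCRF and sends the deviations to the regulator in an XPT file. Protocol 9.1 provides individual listings of all eCRF items, and Protocol 9.3 allows for tabulating reasons for exclusion from each set.

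**Conclusion.** The inconsistency is real and minor. On the literal text, subjects randomized despite failing a criterion are absent from the deviation tables and listings of SAP 8.6, and the safety set is not nested in the randomized set. Disposition under SAP 8.1 is affected only if its wording refers to the defined set, which the SAP leaves open.

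No inference changes. The mITT set carries its own eligibility condition, so the superiority tests are the same either way. Section 8.6 removes critical eligibility failures from the PP set, so the bioequivalence test is the same, although the full PP criteria are not visible. The safety set has no eligibility condition, so the safety summaries are the same.

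The conclusion rests on reading the definition as it stands and on the derivation document not already correcting it. The number of subjects involved is unknown; the 6 to 31 above depend wholly on the assumed 1% to 5%.

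**What to change.** Replace the definition with one along these lines: *all subjects assigned a treatment through the IWRS, regardless of whether they met the eligibility criteria or took study drug, analysed by assigned treatment*. Keep eligibility conditions only in the mITT and PP sets. State in SAP 8.1 that disposition from randomization onward uses this set, with screened subjects counted separately.

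The cost is one sentence in the definition, a clarifying phrase in 8.1, and a check that the population derivation document and flags agree, all before database lock under the SAP's own change control. It needs no new data and changes neither the sample size nor any efficacy or safety analysis.

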### 4.4 Safety Population

All randomized subjects who receive at least one dose of study drug will form the Safety Analysis Set. The Safety Analysis Set will be used for all analyses of safety, tolerability, and background characteristics.

[figure not shown]
### 4.5 Modified intent-to-treat (mITT)

The modified intent-to-treat (mITT) is a subset of the safety analysis set consisting of all randomized subjects who meet all inclusion and none of the exclusion criteria, received at least one dose of study drug and provided efficacy and safety data after one dose of study drug. The mITT set is the basis for testing superiority of each active arm compared to the placebo with respect to primary efficacy endpoint i.e. clinical cure rate.

### 4.6 Per-Protocol (PP) Population

The PP analysis set is the primary analysis set for the assessment of bioequivalence between the test and the reference products.

[figure not shown]

[figure not shown]
Subjects discontinued early for other reasons will be excluded from the PP population, but included in the mITT population, using LOCF.

## 6. HANDLING MISSING VALUES

LOCF will be used to impute missing efficacy data for the following situations.

a.

b.

[figure not shown]

c. Subjects discontinued early for other reasons will be excluded from the PP population

d.

e.

Missing data for other assessment (e.g., safety assessment or baseline assessment) will not be imputed. However, for the purpose of summary, AEs with missing relationship to study drug assessment will be counted as “related”; AEs with missing intensity assessment will be counted as “severe”. Missing intensity and relationship will be presented as is on the individual subject data listing.

## 7. STATISTICAL METHODOLOGY

Unless otherwise explicitly stated, descriptive statistics for continuous variables are: n, mean, median, standard deviation, minimum and maximum. Descriptive statistics for categorical variables are: percentage, and the numerator (n) and the denominator (N) used in the percentage calculation.

### 7.1 Hypotheses and Decision Rules

Two sets of null hypotheses will be used for the primary efficacy endpoint to evaluate the clinical bioequivalence between test product and reference products with respect to the clinical cure rate using Per-Protocol (PP) population. The hypothesis for testing equivalence is stated as below:

#### 7.1.1 Primary Efficacy Analysis

##### (i) Hypothesis for Bioequivalence:

$$H_0: p_T - p_R < -0.20 \text{ or } p_T - p_R > 0.20$$

Versus

$$H_1: -0.20 \leq p_T - p_R \leq 0.20$$

Where  $p_T$  = clinical cure rate of test treatment and  $p_R$  = clinical cure rate of reference treatment.

The null hypothesis for bioequivalence will be evaluated based on the PP analysis set using two one-sided Z-test with Yates correction, each at the 0.05 significance level. In practice, this is equivalent to constructing 90% confidence intervals (CIs) for the difference (test – reference) using a statistical model appropriate for the study design. If both intervals fall completely within the cut-off limits of [-0.20, +0.20] for clinical cure rates in this study, then equivalence is declared. Otherwise, equivalence is not declared.

**(ii) Hypothesis for Superiority:**

$$H_0: p_T = p_P$$

Versus

$$H_1: p_T \neq p_P$$

Where  $p_T$  = clinical cure rate of subjects treated with rifaximin or Xifaxan and  $p_P$  = clinical cure rate of subjects receiving placebo.

The objective of superiority test is to demonstrate that the test product and the reference product performed as expected (i.e. statistically superior to placebo) in the study. Hence, this null hypothesis serves as a validity to check the study sensitivity, after establishing the clinical bioequivalence between the test product and the reference product.

The null hypothesis for superiority analysis will be evaluated based on the mITT analysis set with LOCF for the missing data using a two-sided Z-test test with Yates correction with a significance level of  $\alpha=0.05$ . Differences between the treatment groups and 95% CIs for the difference will be presented.

The tests for superiority will be conducted independently for test and reference products and superiority will be claimed if the two-sided p-value is found to be  $<0.05$  at 5% level of significance for both, test and reference products separately; and the clinical cure rate is higher for the active drug(s) when compared with the placebo arm.

**7.1.2 Hypothesis for Other Efficacy parameters**

Difference between groups in other efficacy endpoints will be examined as supportive/confirmatory analysis base on the following null hypothesis:

For categorical variables:

$$H_0 : P_i = P_j \text{ vs } H_1: P_i \neq P_j$$

Where  $P$  = proportion of subjects meeting the criteria,  $i$  and  $j = 1$  (Test) ,  $2$  (Reference), or  $3$  (Placebo) and  $i \neq j$

For continuous variables:

$$H_0 : \mu_i = \mu_j \text{ vs } H_1: \mu_i \neq \mu_j$$

Where  $\mu$  = group mean/median,  $i$  and  $j = 1$  (Test),  $2$  (Reference), or  $3$  (Placebo) and  $i \neq j$

All tests will be two-sided and performed at the 0.05 significance level. No adjustments will be made for multiplicity testing since all secondary efficacy endpoints are supportive/ confirmatory.

## 7.2 Sample Size Justification

[figure not shown]
The sample size calculation for this study is based on the published literature (CDER statistical review of NDA submission 21-361) and FDA's current guidance (FDA Guidance, 2004) on the clinical endpoint bioequivalence study of Rifaximin 200 mg.

[figure not shown]
Superiority to be concluded when the lower bound of the two-sided 95% CI is greater than zero i.e. the 95% CI does not contain zero.

[figure not shown]
achieve at least 85% power to detect equivalence when the margin of equivalence for clinical cure rate extends from -0.20 to 0.20 (i.e.  $\pm 20\%$ ).

Thus, approximately 618 patient(s) will be enrolled and randomized

[figure not shown]
the overall dropout rate from the randomized patient population to mITT population does not exceed 15%.

subjects in the PP population when the lower and upper 90% CI falls within [-0.20, +0.20].

### 1:1:1 Randomization

Thus, a total of 618 subjects need to be enrolled and randomized

assuming that the dropout rate from the randomized to mITT population does not exceed 15%.

### 7.3 Exposure and Treatment Compliance

Subject compliance will be primarily monitored by counting the study tablets dispensed (Visit 1) and returned (Visit 3) compared to diary entries. Compliance calculation will be based on number of tablets taken (as recorded in the study diary) vs number of tablets subjects are expected to take.

Total extent of exposure to study drug will be measured by total number of tablets taken and duration of exposure calculated as date of last dose minus date of first dose plus 1. Study drug compliance (%) will be calculated as number of tablets taken divided by number of tablets expected to take multiplied by 100. Subjects are considered to have good compliance if the compliance (%) is within the range of ~75% to ~125%, corresponding to 7 to 11 doses.

### 7.4 Interim Analysis

No interim analyses are planned in this study.

### 7.5 Efficacy Analysis

The following primary and secondary variables will be investigated in the evaluation of efficacy:

#### 7.5.1 Primary Efficacy Analysis

The primary efficacy variable is the proportion of subjects who achieve clinical cure within 24 to 48 hours from the time of last dose.

To evaluate the null hypothesis (i) i.e., test for equivalence, the proportion of subjects meeting the clinical cure criteria will be tabulated by treatment group on the PP analysis set with LOCF\* for missing data imputation. The differences between the test product and reference product on the PP analysis set will be estimated and the 90% CIs for the difference will be presented. The 90% CIs will be calculated using Z-test for proportion with Yates' correction as presented below.

$$\begin{aligned}L &= (P_T - P_R) - 1.645 \text{ se} - (1/N_T + 1/N_R)/2 \\U &= (P_T - P_R) + 1.645 \text{ se} + (1/N_T + 1/N_R)/2 \\P_T &= C_T / N_T \\P_R &= C_R / N_R \\se &= \text{SQRT} [P_T*(1-P_T) / N_T + P_R*(1-P_R)/N_R]\end{aligned}$$

Where  $C_T$  and  $C_R$  are number of subjects meeting the clinical cure criteria in the test product and the reference product arm respectively;  $P_T$ ,  $P_R$  are the proportions of clinical cure from the test product arm and the reference product arm, respectively;  $N_T$  and  $N_R$  are total number of subjects in the analysis set from the test product and the reference arm product, respectively;  $se$  = standard error;  $\text{SQRT}$  = square root.

If the upper and the lower CIs are within the range of [-0.20, +0.20], the null hypotheses for clinical bioequivalence will be rejected and it can be claimed that the test product and the reference product are clinically equivalent with respect to the clinical cure rates.

Reasons for clinical failure will also be tabulated by treatment group showing the number and percentage of subjects failed by each criterion.

To evaluate the null hypothesis (ii) i.e., test of superiority, the proportion of subjects meeting the clinical cure criteria will be tabulated based on the mITT analysis set with LOCF for missing data imputation. The differences between each active arm (test and reference) and the placebo group will be tested separately using a two-sided Z-test for proportion using Yates correction; the estimated difference and 95% CIs will be presented.

### **7.5.2 Secondary Efficacy Analysis**

All secondary efficacy endpoints will be tabulated by treatment groups on the mITT and PP populations.

For the secondary endpoint TLUS, defined as the interval beginning with the first dose of study drug and ending with the last unformed stool passed within 48hrs from the time of last dose, summary tables will be presented.

A nonparametric test, Wilcoxon Rank-Sum Test, will be used for comparing the median TLUS difference between two treatment arms at 5% level of significance, without any adjustment for multiplicity. Additionally, Hodges-Lehmann estimate of location shift and Moses 95% confidence intervals will be calculated to assess the magnitude of median TLUS difference between two treatment arms at 5% level of significance.

For microbiological cure rate, summary tables will include number and percentage of subjects in each category; differences between groups (test vs. placebo, reference vs. placebo, and test vs. reference) will be derived along with the 95% CIs for the difference using the Z-test for proportion to test the difference between the treatment groups; the Yates's correction will be applied for the calculation of 95% CIs.

## **7.6 Safety Analysis**

All Safety analysis will be summarized based on safety population and all safety summaries will be provided by treatment group.

### **7.6.1 Adverse Events**

All AEs that occur during the study will be recorded. AEs will be coded using the Medical Dictionary for Regulatory Activities (MedDRA), version 18.1 or higher. Descriptions of

reactions or complaints will include the approximate time of onset, the time the AE ended, the severity of the AE, and the outcome. The Adverse Events (AEs) will be summarized by System Organ Class, preferred term, severity, and relationship to study drug.

All Adverse Event summary tables will list each event, the number of subjects in each treatment group in which the event occurred, and the rate of occurrences. The events will be grouped by System Organ Class and Preferred Term. Frequencies and percentages of patients experiencing TEAEs (Treatment Emergent Adverse Events) will be summarized by system organ class (SOC) and by preferred term within SOC for each treatment group. Additional summaries of AEs by severity and by relation to treatment will be tabulated by SOC and by MedDRA preferred term within SOC.

For AE summary tables, percentages would be based on the number of subjects in safety population in that particular treatment group. If a subject experienced more than one episode of an adverse event, the subject would be counted once for that event. If a patient had more than one adverse event in a system organ class, then the patient would be counted only once in that system organ class.

Serious Adverse Events (other than death but including the Serious Adverse Events temporally associated with or preceding the deaths) will be displayed in a summary table and listed. All Adverse Events or Serious Adverse Events which lead to withdraw from the study will be displayed in a summary table and listings.

